### **9.1.2 Withdrawal of informed consent**

Patients may voluntarily withdraw consent to participate in the study for any reason at any time. Withdrawal of consent occurs only when a patient:

- Does not want to participate in the study anymore,  
and
- Does not want any further visits or assessments,  
and
- Does not want any further study related contacts.

In this situation, the investigator should make a reasonable effort (e.g., telephone, e-mail, letter) to understand the primary reason for the patient's decision to withdraw his/her consent and record this information.

Legal framework of certain countries does not require consent to the use of personal and coded data. However, patients in these countries do retain the right to object to the further use of their personal data.

Study treatment must be discontinued and no further assessments conducted, and the data that would have been collected at subsequent visits may not be collected and will be considered missing.

Further attempts to contact the patient are not allowed unless safety findings require communicating or follow-up.

All efforts should be made to complete the assessments prior to study discontinuation. A final evaluation at the time of the patient's study discontinuation should be made as detailed in the assessment table.

All research results (data) that have already been collected for the study evaluation will continue to be used.

### **9.1.3 Lost to follow-up**

For patients whose status is unclear because they fail to appear for study visits without stating an intention to discontinue or withdraw, the investigator must show "due diligence" by documenting in the source documents steps taken to contact the patient, e.g., dates of telephone calls, registered letters, etc. A patient should not be considered as lost to follow-up until due diligence has been completed or until the end of the study.

### **9.1.4 Study stopping rules**

#### **Overall study stopping rules**

Enrollment in the study will be placed on hold if any of the following occurs cumulatively across all treatment arms:

During Part A:

- 3 or more study drug-related SAEs;
- 6 or more patients experience hypersensitivity reactions or injection reactions of moderate to severe intensity;
- 3 or more patients experience a similar AE, or a similar laboratory finding, which was assessed as CTCAE Grade 3 or 4 and considered as potentially study drug related;
- The sponsor considers that the number and/or severity of AEs, abnormal safety monitoring tests, or abnormal laboratory findings justify putting the study on hold.

During Part B (cumulative):

The study may resume following a safety review by the IDMC, if the investigator and sponsor agree it is safe to proceed.

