## 10 Safety monitoring and reporting

### 10.1 Definition of adverse events and reporting requirements

#### 10.1.1 Adverse events

An adverse event (AE) is any untoward medical occurrence (e.g., any unfavorable and unintended sign [including abnormal laboratory findings], symptom or disease) in a clinical investigation patient after providing written informed consent for participation in the study. Therefore, an AE may or may not be temporally or causally associated with the use of a medicinal (investigational) product.

The investigator has the responsibility for managing the safety of the individual patient and identifying and documenting AEs.

Qualified medical personnel will be readily available to advise on trial-related medical questions or problems.

Throughout the study, the investigator will determine whether any AEs have occurred by evaluating the participant. These events may be directly observed, reported spontaneously by the patient or by questioning the patient at each study visit or by laboratory test findings. Patients should be questioned in a general way, without asking about the occurrence of any specific symptoms.

Note that any symptoms collected by the PROs (see [Section 8.3.3](#)) will not be considered AEs and will not be reconciled with AEs.

Adverse events should be described using a diagnosis whenever possible, rather than individual underlying signs and symptoms. Adverse events must be accompanied by the following information (as far as possible):

1. Intensity, graded according to the Common Terminology Criteria for Adverse Events (CTCAE) version 5.0
2. Its causal relationship to the study treatment. If the event is due to lack of efficacy or progression of underlying illness (i.e., progression of the study indication) the assessment of causality will usually be 'Not suspected.' However, worsening of COVID-19 that exceeds anticipated fluctuations or course of the disease should be documented as AE, and may qualify as an adverse event of special interest (AESI) (see [Section 10.1.4](#)).
3. Its duration (start and end dates) or if the event is ongoing, an outcome of not recovered/not resolved must be reported
4. Whether it constitutes a SAE (see [Section 10.1.2](#) for definition of SAE, and [Section 10.1.3](#) for SAE reporting) and which seriousness criteria have been met
5. All AEs must be treated appropriately. Treatment may include interrupting or withdrawing of study drug
6. Its outcome

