### **10.1.2 Serious adverse events**

An SAE is defined as any AE (appearance of [or worsening of any pre-existing]) undesirable sign(s), symptom(s), or medical condition(s) which meets any one of the following criteria:

- fatal
- life-threatening (see definition below)

Life-threatening in the context of an SAE refers to a reaction in which the patient was at risk of death at the time of the reaction; it does not refer to a reaction that hypothetically might have caused death if it were more severe (please refer to the ICH-E2D Guidelines).

- results in persistent or significant disability/incapacity
- constitutes a congenital anomaly/birth defect
- requires inpatient hospitalization or prolongation of existing hospitalization, unless hospitalization is for:
  - routine treatment or monitoring of the studied indication, not associated with any deterioration in condition

- elective or pre-planned treatment for a pre-existing condition that is unrelated to the indication under study and has not worsened since signing the informed consent
  - social reasons and respite care in the absence of any deterioration in the patient's general condition
  - treatment on an emergency outpatient basis for an event not fulfilling any of the definitions of a SAE given above and not resulting in hospital admission
  - is medically significant, e.g., defined as an event that jeopardizes the patient or may require medical or surgical intervention to prevent one of the outcomes listed above
- Medical and scientific judgment should be exercised in deciding whether other situations should be considered serious reactions, such as important medical events that might not be immediately life threatening or result in death or hospitalization but might jeopardize the patient or might require intervention to prevent one of the other outcomes listed above. Such events should be considered as "medically significant." Examples of such events are intensive treatment in an emergency room or at home for allergic bronchospasm, blood dyscrasias, or convulsions that do not result in hospitalization or development of dependency or abuse (please refer to the ICH-E2D Guidelines).

Any suspected transmission via a medicinal product of an infectious agent is also considered a serious adverse reaction.

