#### **10.1.3 SAE reporting**

To ensure patient safety, every SAE, regardless of causality, occurring after the patient has provided informed consent and until last study visit must be reported to the medical monitor safety desk within 24 hours of learning of its occurrence. Detailed instructions regarding the submission process and requirements are included in the investigator folder provided to each site.

All follow-up information for the SAE including information on complications, progression of the initial SAE and recurrent episodes must be reported as follow-up to the original episode within 24 hours of the investigator receiving the follow-up information. An SAE occurring at a different time interval or otherwise considered completely unrelated to a previously reported one must be reported separately as a new event.

If the SAE is not previously documented in the IB or Package Insert (new occurrence) and is thought to be related to the study treatment, further information may urgently be required from the investigator for health authority reporting. An Investigator Notification (IN) may need to be issued to inform all investigators involved in any study with the same study treatment that this SAE has been reported.

Suspected Unexpected Serious Adverse Reactions (SUSARs) will be collected and reported to the competent authorities and relevant ethics committees in accordance with EU Guidance 2011/C 172/01 or as per national regulatory requirements in participating countries.

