2.8.1 Adverse events (AEs)

Adverse events (AEs) will be coded based on the latest available MedDRA version practically possible (version 23.0 or above) that gives preferred term (PT) and primary system organ class (SOC) information. The MedDRA version will be displayed in the respective output footnotes. AEs will be graded using the common toxicity criteria for adverse events (CTCAE) version 5.0. The number (and percentage) of patients with treatment-emergent

- Treatment emergent AEs (TEAEs)
- Serious adverse events (SAEs)
- AEs of Special Interest (AESIs; see [Section 2.8.1.1](#))

will be summarized by:

- treatment, SOC and PT;
- treatment, SOC, PT, and CTCAE grade; and,
- treatment, Standardized MedDRA Query (SMQ) and PT.

In addition, the following events will be summarized by treatment, SOC and PT as well as by SOC, PT and maximum CTCAE grade:

- TEAEs leading to discontinuation of study drug;
- and,
- TEAEs suspected to be study drug related.

Deaths will be summarized by SOC and PT.

Dot plots of the most frequent TEAEs of CTCAE grade 3 or higher, and serious TEAEs will be provided.

AEs, SAEs, and AESIs will be listed, treatment emergent events will be flagged.

In AE summaries, the primary SOC will be presented alphabetically and the PTs will be sorted within the primary SOC in descending frequency of the highest ensovibep dose. If a patient reported more than one AE with the same preferred term, the AE with the greatest severity will be presented. If a patient reported more than one AE within the same primary system organ class, the patient will be counted only once with the greatest severity at the SOC level, where applicable. An AE with missing CTCAE grade will be included in 'All grades' of the summary tables only.

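### Part A hold rule for clusters of similar severe AEs stops at Grade 4, so a fatal case never graded 3 or 4 does not add to its count of three

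*Protocol*

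**What the plan says.** Protocol 9.1.4 lists four conditions for Part A, counted cumulatively over all arms. Any one of them puts enrollment on hold. They are numbered here in the order listed.

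- Rule 1: "3 or more study drug-related SAEs".
- Rule 2: "6 or more patients experience hypersensitivity reactions or injection reactions of moderate to severe intensity".
- Rule 3: "3 or more patients experience a similar AE, or a similar laboratory finding, which was assessed as CTCAE Grade 3 or 4", with the further condition that the event is considered potentially related to study drug.
- Rule 4 has no number. It applies when "The sponsor considers that the number and/or severity of AEs", or abnormal safety tests or laboratory findings, justify a hold.

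Protocol 10.1.1 sets the grading scale: "Intensity, graded according to the Common Terminology Criteria for Adverse Events (CTCAE) version 5.0". Protocol 10.1.2 lists a fatal outcome among the criteria for an SAE. The rationale for global Amendment 1 says the stopping rules were clarified to follow CTCAE grading and to include laboratory findings.

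Elsewhere the documents leave the top of a grade range open. Protocol 10.1.4 defines AESIs for infusion site and hypersensitivity reactions from Grade 2 upward, and SAP 2.8.1 plans "Dot plots of the most frequent TEAEs of CTCAE grade 3 or higher".

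**The concern.** Rule 3 is the only numeric rule aimed at a cluster of the same severe event, and its grade range is closed at both ends. A patient who dies of that event without it having been graded 3 or 4 is outside the range. The death does count in rule 1, but rule 1 needs three related SAEs of its own, and nothing in 9.1.4 adds the counts of different rules together.

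A cluster that includes a death can therefore miss every numeric trigger, while a milder cluster of the same size meets one. Numeric rules exist so that a hold does not depend on judgment alone. In these patterns it would depend on rule 4.

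**Working it through.** The plan gives no figure to reproduce. The check counts cases and assumes no event rate.

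**Inputs.** The thresholds of 3 for rules 1 and 3, and the grade range of rule 3, come from Protocol 9.1.4. That a fatal AE is an SAE comes from Protocol 10.1.2.

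**Assumptions.**
- All cases are the same AE, one per patient, and all are judged related.
- There are no other related SAEs.
- A fatal case was never graded 3 or 4. The documents do not print the CTCAE scale, so a death is taken to lie above Grade 4.
- Grade 4 cases are serious.
- The AE is not a hypersensitivity or injection reaction, so rule 2 does not apply.

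**Formulas.** Let g3 and g4 be the numbers of Grade 3 and Grade 4 cases, g5 the number of fatal cases, and s3 the number of Grade 3 cases that are serious.

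- Rule 1 triggers if g4 + g5 + s3 ≥ 3.
- Rule 3 as written triggers if g3 + g4 ≥ 3.
- Rule 3 with an open top triggers if g3 + g4 + g5 ≥ 3.

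**Patterns that meet neither rule now but would meet rule 3 with an open top:**

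| g3, g4, g5 | s3 | Rule 1 count | Rule 3 count now | Rule 3 count, open top |
|---|---|---|---|---|
| 2, 0, 1 | 0 | 1 | 2 | 3 |
| 1, 0, 2 | 0 | 2 | 1 | 3 |
| 1, 1, 1 | 0 | 2 | 2 | 3 |
| 2, 0, 2 | 0 | 2 | 2 | 4 |
| 2, 0, 1 | 1 | 2 | 2 | 3 |

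That is 4 patterns if no Grade 3 case is serious and 1 if one is. If all are serious (s3 = g3), rule 1 counts every case and nothing is missed. For comparison, (3, 0, 0) gives a rule 3 count of 3 and triggers now.

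**Upper limit on cluster size.** Let F be the fatal cases, S the serious Grade 3 or 4 cases and N the non-serious Grade 3 or 4 cases. If neither rule triggers, F + S ≤ 2 and S + N ≤ 2. The total is F + S + N = (F + S) + (S + N) − S ≤ 4 − S. The largest cluster without a numeric trigger is therefore 4 patients, or 3 if one non-fatal case is serious. With an open top it is 2.

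**Cross-check without assuming that Grade 4 is serious.** Of the 10 ways to split 3 cases into (F, S, N), 3 escape: (1,0,2), (1,1,1) and (2,0,1). Of the 15 ways to split 4 cases, 1 escapes: (2,0,2). With 5 or 6 cases none escapes. With an open top none escapes at any of these sizes. Every escaping split has at least one death and at least one non-serious case.

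**Triggers lost by the change.** None, because g3 + g4 + g5 is never less than g3 + g4.

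**The case against.** The strongest reply concerns how a fatal case is counted. The rule counts cumulatively and refers to an event that was assessed at a given grade, and Protocol 10.1.1 requires changes in severity to be assessed at each visit. A reader might infer that a case drops out of the count when it moves from severe to fatal. The documents do not say so. An event graded 3 or 4 before death may well remain counted, and on that reading the gap is confined to fatal events never graded 3 or 4. This stands, and the point is limited accordingly.

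The second reply is that deaths are already handled. A related death counts in rule 1. Rule 4 covers both number and severity. Under Protocol 10.1.3, "every SAE, regardless of causality, occurring after the patient has provided informed consent and until last study visit must be reported" within 24 hours, and the IDMC reviews safety. So it would be wrong to infer that the hold rules ignore deaths. These safeguards keep the point small, but a discretionary hold does not correct a numeric rule that can respond less to a worse cluster.

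Third, the missed patterns are narrow. An event is also serious if it "is medically significant, e.g., defined as an event that jeopardizes the patient or may require medical or surgical intervention", and after a related death, further severe cases of the same AE are likely to be judged serious. This stands too: the counts of 4, 1 and 0 show how quickly the gap closes. They are unweighted combinations, not probabilities.

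Two further inferences should be resisted. Rule 2 could be read as Grades 2 to 3 only, which would exclude the worst reactions. But it names no grade, and 10.1.4 describes COVID-19 worsening in similar terms with no sign that worse cases are left out, so a gap in rule 2 is not established. Nor does the SAP contradict the protocol: its dot plots are descriptive and serve a different purpose from an enrollment hold.

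**Conclusion.** The point holds as a minor wording gap in rule 3 for Part A. For AEs other than reactions, clusters of 3 to 4 similar related cases with at least one death and at least one non-serious Grade 3 case can miss every numeric trigger. The size is 4, 1 or 0 patterns according to whether none, one or all of the Grade 3 cases are serious. The conclusion rests on the deaths never having been graded 3 or 4, on Grade 4 cases being serious, and on there being no other related SAEs. If a case graded 3 or 4 earlier still counts after death, such cases create no gap.

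Little Part A enrollment was left to protect. Amendment 1 reports 381 patients treated by 19 October 2021, against a target of at least 400 randomized, so about 400 − 381 = 19 remained to the minimum. The Part B rules are not visible in the public text, and nothing is claimed about them.

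**What to change.** In rule 3 of Protocol 9.1.4, replace the closed range with 'CTCAE Grade 3 or higher'. Keep the count of 3, the pooling across arms and the causality condition. This also settles that a fatal case counts whatever its earlier grade.

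As an optional clarification, let rule 2 say 'of CTCAE Grade 2 or higher' in place of its present intensity wording. The event terms should stay as they are: rule 2 and Protocol 10.1.4 name the reactions differently, and changing the event class is a separate decision.

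The cost is a few words in an amendment. No new data, staff or unblinding is needed, and no cluster that triggers a hold now would stop doing so.

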#### **9.1.5 Early study termination by the sponsor**

The study can be terminated by the sponsor at any time.

Reasons for early termination

- Unexpected, significant, or unacceptable safety risk to patients enrolled in the study
- Decision based on recommendations from applicable board(s) after review of safety and efficacy data
- Discontinuation of study drug development

In taking the decision to terminate, the sponsor will always consider patient welfare and safety. Should early termination be necessary, patients must be seen as soon as possible and treated as a prematurely withdrawn patient. The investigator shall be informed of additional procedures to be followed in order to ensure that adequate consideration is given to the protection of the patient's interests. The investigator or sponsor depending on local regulation will be responsible for informing IRBs/IECs of the early termination of the trial.

#### **9.2 Study completion and post-study treatment**

Study completion is defined as when the last patient finishes their Study Completion visit and any repeat assessments associated with this visit have been documented and followed-up appropriately by the investigator or, in the event of an early study termination decision, the date of that decision.

## 10 Safety monitoring and reporting

### 10.1 Definition of adverse events and reporting requirements

#### 10.1.1 Adverse events

An adverse event (AE) is any untoward medical occurrence (e.g., any unfavorable and unintended sign [including abnormal laboratory findings], symptom or disease) in a clinical investigation patient after providing written informed consent for participation in the study. Therefore, an AE may or may not be temporally or causally associated with the use of a medicinal (investigational) product.

The investigator has the responsibility for managing the safety of the individual patient and identifying and documenting AEs.

Qualified medical personnel will be readily available to advise on trial-related medical questions or problems.

Throughout the study, the investigator will determine whether any AEs have occurred by evaluating the participant. These events may be directly observed, reported spontaneously by the patient or by questioning the patient at each study visit or by laboratory test findings. Patients should be questioned in a general way, without asking about the occurrence of any specific symptoms.

Note that any symptoms collected by the PROs (see [Section 8.3.3](#)) will not be considered AEs and will not be reconciled with AEs.

Adverse events should be described using a diagnosis whenever possible, rather than individual underlying signs and symptoms. Adverse events must be accompanied by the following information (as far as possible):

1. Intensity, graded according to the Common Terminology Criteria for Adverse Events (CTCAE) version 5.0
2. Its causal relationship to the study treatment. If the event is due to lack of efficacy or progression of underlying illness (i.e., progression of the study indication) the assessment of causality will usually be 'Not suspected.' However, worsening of COVID-19 that exceeds anticipated fluctuations or course of the disease should be documented as AE, and may qualify as an adverse event of special interest (AESI) (see [Section 10.1.4](#)).
3. Its duration (start and end dates) or if the event is ongoing, an outcome of not recovered/not resolved must be reported
4. Whether it constitutes a SAE (see [Section 10.1.2](#) for definition of SAE, and [Section 10.1.3](#) for SAE reporting) and which seriousness criteria have been met
5. All AEs must be treated appropriately. Treatment may include interrupting or withdrawing of study drug
6. Its outcome

Relevant conditions apart from COVID-19 infection, which were already present at the time of informed consent should be recorded in medical history of the patient. However, worsening of these conditions after study start should be recorded as an AE.

Adverse event monitoring should be continued until EOS visit (see [Table 8-1](#)). After the EOS, only serious events assessed as related to study drug should continue to be reported, and only to the safety database.

Once an AE is detected, it must be followed until its resolution or until it is judged to be permanent (e.g., continuing at the end of the study), and assessment must be made at each visit (or more frequently, if necessary) of any changes in severity, the suspected relationship to the interventions required to treat it, and the outcome.

Information about adverse drug reactions for the investigational drug can be found in the IB.

Abnormal laboratory values or test results constitute AEs only if they fulfill at least one of the following criteria:

- they induce clinical signs or symptoms
- they are considered clinically significant
- they require therapy

Clinically significant abnormal laboratory values or test results must be identified through a review of values outside of normal ranges/clinically notable ranges, significant changes from baseline or the previous visit, or values which are considered to be non-typical in patients with the underlying disease.

